7.3 Non-invasive imaging

Cyanoacrylate oil used during imaging may lead to skin irritation and itching. There are no known adverse effects to HIFU, RCM or OCT. The systems are CE-marked and FDA-approved. Vivosight complies with FCC Class B and Vivascope with FCC Class A. All systems fulfill the technical specifications set by the Health Authorities in Denmark and are approved by the Medico Technical Department at Bispebjerg Hospital.

7.4 Punch Biopsy and Blood Sampling

Prior to 4 mm biopsy local analgesic will be used to reduce pain. The biopsy may leave a punctiform scar. Needle-pricks associated with injection and blood sampling (preliminary study) are associated with discomfort. The risk of infection is low (<1%), and will be managed with antibiotics provided by the investigator.

8. Safety Considerations

Patients are followed closely in the initial 30 days after treatment and particularly in the first 14 days. Complete tumor removal is ensured through histological analysis at Month 3. In the event of inadequate treatment response at 3 months, or in the event of withdrawal, patients will receive conventional BCC treatment and follow-up according to national guidelines.

8.1 Definitions

- Incident: any unwanted incident after treatment with a medical product occurring during the trial. Treatment and incident need not be related.
- Adverse Event (AE): Any unexpected medical event without known causal relation to the treatment will be reported as an AE. The event can be of any nature, an incident, a symptom or disease that is temporarily linked to the treatment of cisplatin/5-FU/AFL or the combination, whether or not it is considered related to exposure or not.
- Adverse Reaction (AR): A harmful or unforeseen reaction with a known or expected association to cisplatin/5-FU/AFL or the combination will be reported as an AR.
- Serious Adverse Event (SAE): An adverse event that results in death or leads to serious deterioration in the health of a subject, resulting in:
 - A life-threatening illness or injury, OR
 - A permanent impairment of a body structure or a body function, OR
 - Inpatient or prolonged hospitalization, OR
 - Medical or surgical intervention to prevent life-threatening illness or injury or permanent impairment to a body structure or a body function
 - an adverse event that leads to fetal distress, fetal death or a congenital anomaly or birth defect
- Unexpected Serious Adverse Effect (SUSAR): A serious adverse event that is unexpected according to the product summary, but suspected to be treatment-related (cisplatin/5-FU/AFL or the combination), will be reported as an SUSAR.

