8.2 Documenting and Reporting Adverse Events (AE) and Adverse Reactions (AR)

The investigators are responsible for routine assessments of AEs and ARs. All clinical complaints, symptoms, or signs that meet AE or AR definitions will be documented in the study record and the patient's medical record. Erythema and/or edema are anticipated sequelae of treatment; LSRs included in the LSR Grading Scale are reported as LSRs and not as AEs in the CRF, even if they require treatment. All AEs and ARs are described according to duration (start and end date), severity, association with drugs, whether further treatment is required and whether the AE has led to a serious adverse event. The location of the event is recorded as either "treated area" or "non-treated area". AEs and ARs will be followed until they have resolved.

The severity of an AE/AR is graded as:

- Mild: AE is transient and does not affect daily activities
- Moderate: AE causes patient discomfort and affect daily activities
- Severe: AE affect the patient's daily activities to a significant degree and may mean invalidity/incapacity for work or else be life-threatening.

The outcome of an AE/AR is described as:

- Resolved
- Improvement without sequelae
- Improvement with sequelae
- Persistent, follow-up necessary
- Persistent, follow-up not necessary

The investigators assessment of whether an AE is associated with the trial medication is classified as follows:

- Yes: an AE which after careful evaluation has a temporal association with the treatment and is in all probability related to the trial medication.
- No: an AE which after careful evaluation is definitely judged to be attributable to an external cause (disease, environmental exposure etc.) treatment and is in all probability related to the trial medication.

8.3 Documenting and Reporting of Serious Adverse Events (SAE) and Unexpected Serious Adverse Reactions (SUSAR)

The investigator is responsible for reporting all SAEs after the patient has signed the consent form until the final control visit. SAEs are reported within 24 hours to sponsor-investigator [name]

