9.1 Sample size

The primary objective of this explorative trial is to investigate tolerability of AFL-assisted cisplatin+5-FU to ensure that intolerable/severe or serious related adverse events remain minimal for the observed efficacy. While no formal statistical calculation has been performed, 12 superficial and 12 nodular BCCs in 24 subjects are considered sufficient to estimate benefit/risk of the treatment.

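### The AE, AR, SAE and causality definitions in Sections 8.1 and 8.2 contradict each other and must be reconciled, because the Section 9.1 objective on severe or serious related events rests on them

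*Combined protocol and SAP*

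**What the plan says.** Section 8.1 of the combined protocol and SAP defines an AE in two sentences. The first reads "Any unexpected medical event without known causal relation to the treatment will be reported as an AE". The second covers anything linked in time to the treatment, "whether or not it is considered related to exposure or not".

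The next item sets up the AR: "A harmful or unforeseen reaction with a known or expected association to cisplatin/5-FU/AFL or the combination will be reported as an AR". An SAE is then "An adverse event that results in death or leads to serious deterioration in the health of a subject", with a list of seriousness criteria and no mention of ARs. A SUSAR is "A serious adverse event that is unexpected according to the product summary, but suspected to be treatment-related".

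Section 8.2 gives two causality classes. 'Yes' is for an AE that "has a temporal association with the treatment and is in all probability related to the trial medication". 'No' is for an AE that "is definitely judged to be attributable to an external cause (disease, environmental exposure etc.) treatment and is in all probability related" to the trial medication. Section 8.2 also records reactions on the local skin reaction (LSR) scale as LSRs rather than as AEs, even when they need treatment.

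Section 8.3 requires every SAE to reach the sponsor-investigator within 24 hours, and uses the product summaries to decide whether an SAE is unexpected. Section 9.1 describes the objective as ensuring that "intolerable/severe or serious related adverse events remain minimal" for the efficacy seen.

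**The concern.** The two sentences of the AE definition cannot both govern. Under the first, an expected reaction with a known link is not an AE. It goes to the AR class, which has no serious tier. Under the second, the same event is an AE and, if serious, an SAE. An investigator who applies the first sentence and the AR item literally could file a serious expected reaction as an ordinary AR and give no 24-hour notice.

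The causality field has a separate fault. The 'No' class asserts both an external cause and a probable link to the medication. Between an event that is definitely external and one that is very probably related, there is no place for one that is possibly related.

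Tolerability is the primary purpose of the trial, and Section 9.1 frames it through related events that are severe or serious. Those two attributes, relatedness and seriousness, are the ones whose definitions conflict.

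**Working it through.** The plan states no figure on this point, so the check is to route five kinds of event through the rules as written.

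| Event | First AE sentence plus AR item | Second AE sentence plus rest of Section 8 |
|---|---|---|
| 1. Serious, unexpected, unrelated | AE, so SAE | AE, so SAE |
| 2. Serious, unexpected, suspected related | AE (the link is suspected, not known), so SAE and SUSAR | AE, so SAE and SUSAR |
| 3. Serious, expected, known link, not on the LSR scale | AR; SAE status not stated | AE, so SAE with 24-hour notice |
| 4. Serious reaction on the LSR scale | LSR, not an AE in the CRF; no exception for serious cases | The same |
| 5. Possibly related AE | Neither 'Yes' nor 'No' | The same |

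**Rows 1 and 2.** Both readings agree. The first sentence excludes only a known causal relation, so even the narrow reading admits a serious event whose link is suspected.

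**Row 3.** The readings diverge here. Two places support the broad reading. The SUSAR definition makes some SAEs treatment-related, and the 8.3 test of whether an SAE is unexpected makes sense only if some SAEs are expected. The SUSAR definition does not settle the row by itself, because it requires unexpectedness. The 8.3 test does imply that expected SAEs exist, but by inference and not by definition. The recording list in 8.2 applies to both AEs and ARs, yet its seriousness item names only the AE.

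Such events are conceivable. Section 7.2 anticipates erosion, notable blistering or ulceration, infection and allergy. None of these is among the LSR items in Section 6.1 (erythema, edema, flaking, crusting/scabbing, pustulation), so their handling depends on the AE and AR definitions.

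**Row 4.** This gap exists whichever AE sentence governs, because 8.2 keeps LSR-scale items out of the AE record and says nothing about those that meet a seriousness criterion.

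**Row 5.** The 'No' wording repeats the end of the 'Yes' wording, which looks like a copying slip. Removing it cures the contradiction but still leaves possibly related events unassigned.

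**Scale.** Section 9.1 plans 12 + 12 = 24 patients. One patient with a misclassified serious event is 1/24 = 4.2% of the trial, or 1/12 = 8.3% of one tumor subtype. These figures show the weight of a single event, not its probability.

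**The case against.** The strongest reply is that Section 8 read as a whole already uses the broad meaning. The second AE sentence disregards relatedness, the 'Yes' class lets an AE be related, a SUSAR is a related SAE, expectedness is judged after an event is already an SAE, and the 24-hour duty covers all SAEs without a filter. Much of this stands, and it rules out several stronger readings:

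- A reader might infer that serious related adverse events cannot exist under these definitions, or that expected serious reactions are excluded from SAE reporting. The provisions just listed contradict both. Inclusion is implied but not stated.
- A reader might infer that the Section 9.1 count is pushed toward zero. Nothing shows that. Severity is graded for AEs and ARs alike, so severe related events are recorded under either heading.
- A reader might take the expected frequencies of erosion or scabbing in Section 7.2 as the size of the gap. Those are expected incidences, with no statement that any case would be serious, and scabbing is an LSR item.
- A reader might infer that expedited reporting to the authority would be missed. Section 8.3 requires that only for SUSARs. For a reaction that the product summaries list as expected, only the 24-hour notice to the sponsor-investigator is at stake.

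It is also fair to say that the primary outcomes in Section 6.1, the LSR scores and named side effects, are collected directly, and that ARs are documented and go into the final report under Section 8.4. Routine recording is therefore not in doubt. What the reply does not cure is the conflict between the two AE sentences, the silence on serious ARs and serious LSRs, and the faulty causality classes.

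**Conclusion.** The concern holds as an internal contradiction in operative safety rules. The two AE sentences conflict. The plan does not state that SAE covers serious ARs, although other provisions imply it. The 'No' class contradicts itself, and possibly related events have no class. Followed literally, the text permits a serious expected reaction to be filed as a non-serious AR, or an event to be left without a usable causality code.

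The size cannot be put as a number of events, because the documents give no rate of serious events. What is affected is the seriousness and relatedness classification behind the Section 9.1 objective, and the 24-hour notice. The limit to the 24-hour notice assumes that the reaction is expected under the product summaries, which are not part of the documents. The correction should be made because it is cheap and because, with at most 24 patients, each serious event weighs heavily in the benefit/risk judgement.

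**What to change.** Revise Sections 8.1, 8.2 and 9.1 and the matching CRF fields:

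1. Define an AE as any untoward medical occurrence, regardless of expectedness or relation.
2. Define an AR as the subset of AEs with at least a reasonable possibility of a link to the treatment.
3. State that SAE covers any AE or AR, and any reaction recorded on the LSR scale, that meets a seriousness criterion.
4. Delete the erroneous clause at the end of the 'No' causality class.
5. Add a 'possible' class and count it as related.
6. State that the Section 9.1 objective is assessed on related AEs plus ARs, counting each event once.

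The cost is protocol and CRF wording, and possibly slightly higher reported event counts, since possibly related events and serious LSRs would now be counted.

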8.2 Documenting and Reporting Adverse Events (AE) and Adverse Reactions (AR)

The investigators are responsible for routine assessments of AEs and ARs. All clinical complaints, symptoms, or signs that meet AE or AR definitions will be documented in the study record and the patient's medical record. Erythema and/or edema are anticipated sequelae of treatment; LSRs included in the LSR Grading Scale are reported as LSRs and not as AEs in the CRF, even if they require treatment. All AEs and ARs are described according to duration (start and end date), severity, association with drugs, whether further treatment is required and whether the AE has led to a serious adverse event. The location of the event is recorded as either "treated area" or "non-treated area". AEs and ARs will be followed until they have resolved.

The severity of an AE/AR is graded as:

- Mild: AE is transient and does not affect daily activities
- Moderate: AE causes patient discomfort and affect daily activities
- Severe: AE affect the patient's daily activities to a significant degree and may mean invalidity/incapacity for work or else be life-threatening.

The outcome of an AE/AR is described as:

- Resolved
- Improvement without sequelae
- Improvement with sequelae
- Persistent, follow-up necessary
- Persistent, follow-up not necessary

The investigators assessment of whether an AE is associated with the trial medication is classified as follows:

- Yes: an AE which after careful evaluation has a temporal association with the treatment and is in all probability related to the trial medication.
- No: an AE which after careful evaluation is definitely judged to be attributable to an external cause (disease, environmental exposure etc.) treatment and is in all probability related to the trial medication.

8.3 Documenting and Reporting of Serious Adverse Events (SAE) and Unexpected Serious Adverse Reactions (SUSAR)

The investigator is responsible for reporting all SAEs after the patient has signed the consent form until the final control visit. SAEs are reported within 24 hours to sponsor-investigator [name]

[name]. The investigator is obliged to undertake follow-up consultations until the SAE/SUSAR has been resolved or in the case of permanent disability, stabilized. The product summary for Cisplatin Accord and Efudix are used to determine whether or not a SAE is unexpected. All SAEs and SUSARs are recorded in the patient's medical record and on a separate sheet of the CFR. SUSARs with a fatal or life-threatening outcome are to be reported to the Danish Health and Medicine Authority within 7 days after the reveal and a report on the development of the SUSAR latest 8 days after being reported to the Danish Health and Medicine Authority, while other SUSARs are to be reported within 15 days. Reporting is performed using the e-form on the Danish Health and Medicine Authority website.

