6.1 Primary Outcome

Tolerability measured as:

I) Local Skin Reactions (LSRs)

Non-blinded, clinical evaluation of erythema, edema, flaking, crusting/scabbing and pustulation in treated areas will be performed by a physician using a FDA-approved 0-4 point LSR scale at Days 1, 5, 14 and 30 after AFL exposure (Appendix 1). Standardized,

clinical photographs are taken to document LSRs at each visit.

II) Side Effects

Non-blinded, clinical evaluation of prolonged erythema or edema, hyper- or hypopigmentation, scarring and infection will be evaluated up to 3 months after initial AFL treatment.

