8.4 End of Trial Reporting

At the end of the trial, a final report with all AEs, ARs, SAEs, and SUSARs is handed to the Danish Health and Medicine Authority and the Regional Committee on Health Research Ethics, latest 90 days after conduction. If the trial ends ahead of schedule, a report will be submitted to the above-mentioned instances within 15 days. The results from the trial will also be sent to the Danish Health and Medicine Authority and the Regional Committee on Health Research Ethics latest one year after completion.

9. Statistics

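### Section 8.2 keeps scale-listed local skin reactions out of AE recording with no exception for serious or persistent cases, which conflicts with the AR definition in 8.1 and leaves their safety route unstated

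*Combined protocol and SAP*

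**What the plan says.** Section 6.1 makes LSRs the first component of the primary outcome: "clinical evaluation of erythema, edema, flaking, crusting/scabbing and pustulation in treated areas will be performed by a physician", using a "0-4 point LSR scale at Days 1, 5, 14 and 30 after AFL exposure". The second component, side effects up to 3 months, lists prolonged erythema or edema, pigment change, scarring and infection.

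Section 8.2 then separates the scale from safety recording: "LSRs included in the LSR Grading Scale are reported as LSRs and not as AEs in the CRF, even if they require treatment". The same section requires complaints, symptoms and signs that meet the AE or AR definition to be documented with dates, severity, drug association, treatment required and outcome, and adds that "AEs and ARs will be followed until they have resolved".

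The definitions in section 8.1 matter here. For an AR: "A harmful or unforeseen reaction with a known or expected association to cisplatin/5-FU/AFL or the combination will be reported as an AR". For an SAE: "An adverse event that results in death or leads to serious deterioration in the health of a subject, resulting in", followed by the list of criteria. A SUSAR is in turn defined as a kind of serious adverse event.

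Section 8.4 promises the authority and the ethics committee "a final report with all AEs, ARs, SAEs, and SUSARs". Section 9.1 frames the objective of investigating tolerability as being "to ensure that intolerable/severe or serious related adverse events remain minimal for the observed efficacy".

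**The concern.** For a treatment applied to the skin, the reactions most likely to become intolerable are the local ones, and section 4 already treats severe LSRs as a possible reason to include fewer patients. Scoring expected reactions on their own scale is reasonable. The difficulty is that the exclusion from AE recording has no stated upper limit. It applies whatever the seriousness or duration, and explicitly when the reaction needs treatment.

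At stake is information that the LSR scale does not carry: whether the reaction met an SAE criterion, whether it needed treatment, how it affected daily activities, how it ended, and what happened after Day 30. Section 9.1 states its objective in terms of severe or serious related adverse events. The plan does not say whether an LSR of that kind belongs in that statement.

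**Working it through.** There is no calculation in the plan to reproduce: section 9.1 gives 24 subjects and says that no formal calculation was done. The check is a comparison of passages, with simple arithmetic on the visit schedule.

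**Step 1. Scope of the rule.** The carve-out covers signs on the LSR scale, which section 6.1 lists as five. Erosion, blistering and ulceration, which section 7.2 also anticipates, are not among them; nor are infection and scarring. Those remain reportable in the ordinary way.

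**Step 2. Routes for a serious, treated or persistent LSR.**

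| Destination | What gives access | Does an LSR qualify? |
|---|---|---|
| AE record | AE definition in 8.1 | No, excluded by 8.2 |
| AR record | AR definition in 8.1 | Yes by definition if harmful; 8.2 does not mention ARs when it excludes LSRs |
| SAE, SUSAR | Both defined through adverse event in 8.1 | No explicit route; 8.3 requires all SAEs to be reported and states no LSR exemption |
| Follow-up until resolved | Stated for AEs and ARs in 8.2 | Only if treated as an AR |
| Final safety report | AEs, ARs, SAEs, SUSARs in 8.4 | Only if treated as an AR or SAE |

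If the AR definition is applied as written, harmful LSRs have to be recorded as ARs and the carve-out does very little. If the carve-out is meant to cover ARs too, it overrides the definition without saying so. Sections 8.1 and 8.2 need reconciling either way. Even AR status would not give an explicit path to SAE, because 8.1 defines seriousness only for adverse events.

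**Step 3. Capture after Day 30.**

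| Sign | LSR scale, to Day 30 | Side-effect list, to Month 3 |
|---|---|---|
| Erythema | Yes | If prolonged |
| Edema | Yes | If prolonged |
| Flaking | Yes | No |
| Crusting/scabbing | Yes | No |
| Pustulation | Yes | No (infection is listed, pustulation is not) |

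Three of five signs therefore have no scheduled capture after Day 30. Taking Month 3 as Day 90, the interval is 90 − 30 = 60 days. With the ±5-day windows in the schedule it runs from (90 − 5) − (30 + 5) = 50 to (90 + 5) − (30 − 5) = 70 days. I do not rely on the Month 3 column of the schedule table, which may have been damaged in extraction; section 6.1 and Appendix 1 both end LSR scoring at Day 30.

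**Step 4. Repeat treatment.** Section 3.3 offers a second course on Day 30 if tumor persists. The first course is followed by four LSR gradings (Days 1, 5, 14 and 30). The second is followed by none: the visit list in section 3.4 (Study Duration and Schedule) has no visit between Day 30 and Month 3. Section 6.1 counts days from AFL exposure, which might be read as restarting the clock, but section 6.3.1 counts from baseline and no visits are provided for a second series.

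**The case against.** The strongest reply is that very little need be lost. LSR severity and duration are primary outcome I, so they will be analysed and published. Severe LSRs can curtail inclusion under section 4. Section 8.4 also sends the trial results to the authority and the ethics committee within one year. The carve-out names AEs only, so a harmful LSR can still be an AR, with follow-up to resolution and a place in the final report. Section 8.3 requires all SAEs. Prolonged erythema and edema are followed to Month 3 in their own right.

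Much of this stands, and it rules out stronger readings. A reader might infer that the rule lets severe local reactions escape the safety system altogether, or that the trial could report no severe related adverse event while every participant had a severe, treated LSR. The documents do not support that as a stated consequence: it requires ARs to be read into a sentence that omits them, and the LSR grades would appear in the primary results anyway. A reader might also size the problem from the incidences in section 7.2. The erythema and edema figures there (94-100% and 33-99%) are for mild to moderate reactions, and no rate is given for severe, treated or unresolved ones. Nor does section 9.1 contain a count from which LSRs could be missing; it states an objective.

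The reply does not resolve the conflict between 8.1 and 8.2 or supply the missing SAE route, and it does not provide any capture after Day 30 for the three signs.

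**Conclusion.** The point holds as an unreconciled recording rule with a gap in late capture. The plan does not say whether an LSR that is serious, needs treatment or persists is also handled as an AR or SAE, and the sections that should settle this disagree.

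Its size can be given only as coverage: three of five signs unscheduled for about 60 days (50 to 70 with the windows), and no LSR gradings after a repeat course against four after the first. This rests on taking Month 3 as Day 90 and on the visit list being complete. How many participants would be affected is unknown; section 7.2 expects local effects to be likely to resolve within 30 days, so it may be few.

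Primary outcome I to Day 30 is not undermined. The change is nevertheless worth making, because tolerability is the primary outcome, section 11 says the combination has not been tested topically in patients before, and the amendment is small.

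**What to change.** Keep LSR grading as it is. In section 8.2, delete the closing clause that extends the exclusion to reactions needing treatment, and state that an LSR is also recorded as an AR, and as an SAE where applicable, when it:

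- meets an SAE criterion in 8.1;
- requires treatment;
- leads to withdrawal; or
- is unresolved at the Day 30 assessment, or arises after it (including after a repeat treatment).

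Apply the existing 8.2 fields, follow-up to resolution and 8.4 reporting to these events, and include them in the section 9.1 benefit/risk statement. Cross-reference erythema or edema already recorded as prolonged, so that it is not counted twice. Reconcile 8.1, 8.2, 8.4 and 9.1 with this wording.

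I would not add a trigger based on the highest score, because the 0-4 scale is given only four labels (none, mild, moderate, severe) and its top point is undefined. A trigger for spread beyond the treated area is also unnecessary: LSRs are scored in treated areas, and 8.2 already records whether an event lies outside them.

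The cost is amended wording and a trigger box on the CRF page, more AR and AE entries, a less favourable safety table, and possibly an unscheduled follow-up contact for unresolved cases, since no visit falls between Day 30 and Month 3.

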5.2 Intervention Details

- **Ablative Fractional Laser (AFL):** Laser irradiation will be performed using the UltraPulse® laser system with DeepFx handpiece (Lumenis, Santa Clara, USA) which is a 10,600 nm CO₂ laser CE-marked for dermatological use. The procedure is expected to take 15 min.
- **Cisplatin Solution:** The topically-applied cisplatin solution (Accord Healthcare Limited A/S) is approved for commercial use and is administered intravenously at significantly higher doses in the conventional oncological setting. The drug will be provided by the department of Dermatology at Bispebjerg Hospital. 1 ml contains 1 mg cisplatin (0.1%). Other ingredients are sodium chloride and sterile water. For the study, the drug will be supplied in labelled, 3 ml blunt tipped syringes (preprepared by the hospital pharmacy pending a

contractual agreement) and will be light protected and stored at room temperature. The solution will in this study be applied topically for 60 min.

- **Efudix® 5-FU Cream:** The cream (Meda Pharmaceuticals A/S, UK) is used commercially for topical use where standard regimens for BCC consist of twice daily application for 4-6 weeks. The cream sold under special license and is provided via the department of Dermatology at Bispebjerg Hospital. The drug is packaged in tubes of 20 grams and stored at 5 degrees. 1 mg contains 50 mg 5-FU (5%). Other ingredients are stearyl alcohol, vaseline, polysorbate 60, propylene glycol, methyl parahydroxybenzoate, propyl-parahydroxybenzoate and purified water. Topical application under occlusion for up to 7 days will be used on treated area.

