6.3.3 Histology

At the 3 month visit, a 4 mm punch biopsy will be taken centrally in treatment area for histological verification of tumor clearance. Biopsy tissue will undergo standard sectioning and histological evaluation by a board-certified pathologist at the Department of Pathology, Bispebjerg Hospital. If tumor residual/recurrence is confirmed, test areas will be treated according to clinical guidelines.

7. Potential Risks and Side Effects

In general, no serious or systemic side effects are assumed but will be reported to the relevant authorities if they occur. Topical 5-FU cream and AFL are used daily at Bispebjerg Hospital's dermatological clinic and are well-tolerated. Cisplatin has previously been examined in a live pig study where no systemic drug uptake or effects were observed. Any obtained information about adverse effects related to this study will be recorded systematically.

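### The causality classes in Section 8.2 contradict themselves and omit possibly related events; separately, judging cisplatin expectedness from an intravenous product's summary could take a serious systemic reaction out of expedited reporting

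*Combined protocol and SAP*

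**What the plan says.** **Causality (Section 8.2).** The classification is introduced with "The investigators assessment of whether an AE is associated with the trial medication is classified as follows". There are two classes. *Yes* is an event that "has a temporal association with the treatment and is in all probability related to the trial medication". *No* is an event "definitely judged to be attributable to an external cause (disease, environmental exposure etc.) treatment and is in all probability related to the trial medication". There is no class for possible, unlikely or not assessable.

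**SUSAR definition (Section 8.1).** A serious event is a SUSAR if it is unexpected by the product summary and "suspected to be treatment-related (cisplatin/5-FU/AFL or the combination), will be reported as an SUSAR".

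**Expectedness and time limits (Section 8.3).** "The product summary for Cisplatin Accord and Efudix are used to determine whether or not a SAE is unexpected". Fatal or life-threatening SUSARs go to the Danish authority within 7 days, "while other SUSARs are to be reported within 15 days". All SAEs go to the sponsor-investigator within 24 hours.

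**The cisplatin product (Section 5.2, Intervention Details).** It "is administered intravenously at significantly higher doses in the conventional oncological setting".

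**Expected risk (Sections 7, 7.2 and 11).** Section 7 says that "no serious or systemic side effects are assumed but will be reported to the relevant authorities if they occur", without a time limit. Section 7.2 does not anticipate the side effects of intravenous cisplatin plus 5-FU. Section 11 says that the intravenous profile does not carry over to this route, and that the treatment has not been tried in patients before.

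**Final report (Section 8.4).** All AEs, ARs, SAEs and SUSARs are reported to the authority and the ethics committee at most 90 days after the trial. After early termination the limit is 15 days.

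**The concern.** The two parts are independent.

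**(a) Causality.** An investigator who follows Section 8.2 literally cannot use *No*, and has nowhere to put an event that is possibly related. The label then depends on how each investigator improvises. Section 9.1 describes the primary objective as keeping severe or serious *related* adverse events minimal, and at most 24 patients are planned, so a few inconsistently labelled events would be visible in the safety description.

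**(b) Expectedness.** The protocol sets the intravenous profile aside when it describes risk, but uses the summary of an intravenous product to decide what counts as expected. A suspected serious systemic reaction would contradict the premise of negligible systemic exposure, which rests on pig data. In the first trial of this treatment in patients, the authority would need to hear of such a reaction early. The expectedness rule could class it as expected and so remove the expedited report.

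**Working it through.** The protocol gives no figure to reproduce here. Part (a) and the first half of (b) are checks of wording; the second half of (b) is date arithmetic.

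**(a) Do the two classes cover every event?** The three levels below are a scale used for this check; the protocol does not define them.

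| Investigator's judgement | Meets *Yes*? | Meets *No* as printed? | Meets *No* without the copied ending? |
|---|---|---|---|
| Probably related | Yes, if also temporally associated | No: not definitely external | No |
| Possibly related | No: not probable | No | No: not definitely external |
| Definitely external | No | No: must also be probably related | Yes |

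As printed, *No* can never be met. With the ending deleted, the middle row still has no class.

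Section 8.1 differs from 8.2 in two ways:

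- *Threshold.* 8.1 asks for suspicion; 8.2 asks for probability. A possibly related serious event can be suspected under 8.1 without being *Yes* under 8.2.
- *Scope.* 8.1 names cisplatin, 5-FU, the laser (AFL) and the combination. 8.2 asks about the trial medication only; the laser can enter only through the temporal link with treatment.

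**(b) How a listed reaction leaves the expedited route.**

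1. A SUSAR must be both unexpected and suspected related (8.1).
2. Expectedness is read from the product summaries (8.1, 8.3).
3. The cisplatin product is an intravenous one (5.2, Intervention Details).
4. If its summary lists a given serious systemic reaction, that reaction is expected, so it is not a SUSAR.
5. The 7- and 15-day limits apply to SUSARs only (8.3).
6. The next dated safety report to the authority is the final report (8.4).

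**Latest date of that report.** Inputs are the planned dates in the study schedule (Section 3.4): treatment start 1 March 2018, final patient treatment 1 December 2018, final control visit 1 March 2019. Assumption: the 90 days in 8.4 run from the final control visit.

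1 March 2019 + 90 days = 30 May 2019.

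Days to deadline = (days from reaction revealed to 1 March 2019) + 90.

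| Reaction revealed | Days to 30 May 2019 | Later than a 7-day limit by | Later than a 15-day limit by |
|---|---|---|---|
| 1 March 2018 | 365 + 90 = 455 | 448 | 440 |
| 1 December 2018 | 90 + 90 = 180 | 173 | 165 |
| 1 March 2019 | 0 + 90 = 90 | 83 | 75 |

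These compare deadlines. They do not estimate an actual delay.

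**The case against.** **Part (a) is a copying slip with little consequence.** The SUSAR trigger in 8.1 does not use the 8.2 class. All SAEs reach the sponsor-investigator whatever their causality, all events enter the final report, and the primary outcome of local skin reactions and side effects does not use the label. Section 9.1 sets no threshold on related events. All of this stands and limits the size of the point. It does not close the gap, which remains after the slip is corrected.

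**Laser reactions have another route.** The adverse reaction definition in 8.1 includes known or expected reactions to the laser, and 8.2 requires adverse reactions to be recorded. This stands for known laser reactions, but does not cover a merely possible one.

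**Part (b) rests on an unseen summary and is a tension rather than a contradiction.** Sections 8.1 and 8.3 agree with each other, 7.2 and 11 describe risk rather than define a reporting term, and a reaction in neither summary would count as unexpected. It is fair that (b) is conditional. But reading expectedness from a profile the protocol says does not apply is a mismatch the protocol itself should resolve.

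**Other safeguards exist.** Up to 6 patients give one blood sample 24 hours after treatment (Section 3.5). Section 10.1 commits to GCP, Section 10.2 allows monitoring, and Section 7 promises reporting. These bear on how likely the problem is; none supplies a dated report to the authority for such a reaction.

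**The day counts are upper limits.** They need a listed reaction, no earlier voluntary report and no early termination; 455 days also places the reaction on the first treatment day. Agreed, and they should be read that way.

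**The proposed wording lowers the causality threshold.** True, and other wording could close the gap. This one matches the suspicion standard already in 8.1.

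**Conclusion.** The concern holds; this should be fixed.

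(a) is certain from the text. *No* is unusable as printed, and after the obvious correction a possibly related event still has no class. The effect is on the consistency of the related label, not on the SUSAR trigger or the primary outcome.

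(b) is certain as a mismatch between the expectedness reference and the protocol's own account of risk. Its consequence is conditional on the cisplatin summary listing the reaction in question. If it does, the last dated obligation to inform the authority moves from 7 or 15 days to as much as 455, 180 or 90 days for the three dates examined, assuming the planned calendar and that the 90 days run from the final visit. The sponsor-investigator may report sooner, and still hears of every SAE within 24 hours.

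No change in the trial's conclusions is shown.

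**What to change.** **Section 8.2 and the CRF.** In *No*, delete everything after the bracketed examples of external causes. Then make the two classes exhaustive: *Yes* if there is a reasonable possibility of relation to cisplatin, 5-FU, AFL or the combination; *No* otherwise. Uncertain events then count as related, in line with 8.1.

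**Sections 8.1 and 8.3.** Reconcile the expectedness reference with Sections 7, 7.2 and 11 by stating that serious systemic toxicity listed only for intravenous use is not treated as expected for this topical route.

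**Cost.** Protocol and CRF wording, and possibly a few more events labelled related or reported as expedited. Sample size and analysis are unchanged.
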